- p. To be completed by parent(s)/caregiver(s) on the electronic device (see [Attachment 7](#) [nasal swab log]), if applicable. Refer to Section 9.2.1 for detailed information.
- q. Body temperature to be measured by parent(s)/caregiver(s) and recorded on the electronic device (see [Attachment 8](#) [temperature log]). In case antipyretics are used, body temperature should be measured immediately before or >4 hours after giving antipyretics. Parents/caregivers should be instructed accordingly.
- r. On the day of discharge, if discharged in the morning, only the evening assessment of the bid schedule should be recorded in the temperature log on the electronic device.
- s. Systolic and diastolic blood pressure need to be measured sitting or supine (preferably the same position at each measurement) after at least 5 minutes of rest.
- t. Physical examination of all body systems includes length and head circumference and body weight measurement and skin examination.
- u. Directed physical examination includes respiratory system, nose, ear, throat, facial, and neck lymph nodes, and skin examination.
- v. Triplicate 12-lead ECGs will be obtained, approximately 1 minute apart and preferably all within 5 minutes. ECGs may be repeated at the discretion of the investigator. ECGs will be obtained in a supine position after 5 minutes of rest. If an ECG is scheduled at the same timepoint as other assessments, the ECG should be performed first.
- w. Samples for clinical laboratory assessments will be collected and analyzed at a central laboratory. Leftover blood samples collected for other testing may be used for exploratory biomarker analyses, at discretion of the sponsor.
- x. Urinalysis will be performed using dipsticks provided by the central laboratory. In case of abnormalities, the urine sample will be shipped to the central laboratory for flow cytometric and/or microscopic evaluation(s).
- y. Adverse events related to the use of the biosensor reported during the substudy will be recorded in the eCRF of the main study.

Note: Additional unscheduled visits in case of lab abnormalities, ECG abnormalities, need for clinical follow-up of (an) AE(s) can be scheduled at the discretion of the investigator.

COHORT 2 SUBJECTS RECRUITED AFTER PROTOCOL AMENDMENT 4^a

Phase	Screening	Treatment Phase							Follow-up ^b					
		1	2	3	4	5 (±1)	6-7	8 (+1)	9-13	14 (±1)	15-20	21 (±3)	22-27	28 (±3) End-of-study

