	Screening / Predose On-site	Treatmen t On-site		On-site visit ^d		On-site visit ^d		On-site visit ^d		On-site visit ^d		On-site visit ^d		Phone visit/ Conditional ^e On-site visit ^d
ECG (triplicate 12-lead) ^{bb}	X	X ^{gg}		X ^{gg}				X				X ^{gg}		(X) ^{o,gg}
Clinical Laboratory Assessments														
Blood sampling for hematology and biochemistry ^{cc}	X ^{hh}							X ^{hh}				X		(X) ^o
Urinalysis ^{dd}	X							X				X		(X) ^o
Pharmacokinetics														
Blood sampling for pharmacokinetics of JNJ-53718678 ^{ee}		X ⁱⁱ		(X) ⁱⁱ		(X) ⁱⁱ								
Acceptability/Palatability														
Acceptability/ palatability questionnaire for parent(s)/caregiver(s)								X						
Ongoing Subject Review														
Adverse events ^{ff}	X	X	X	X	X	X	X	X	X	X	X	X	X	X
Concomitant medication	X	X	X	X	X	X	X	X	X	X	X	X	X	(X) ^o

- When subjects are hospitalized during the course of the study, the reason for hospitalization should be recorded and every effort should be made by the investigator to perform all the assessments as indicated in the **TIME AND EVENTS SCHEDULE**, if practically feasible.
- In case subjects prematurely discontinue study drug treatment for any reason (except withdrawal of consent), the parent(s)/caregiver(s) will be asked to continue with the subject's remaining study visits and assessment schedule, or, at a minimum, to return with the subject to the site for a Withdrawal and a Safety Follow-up Visit. At the Withdrawal and Safety Follow-up Visits, the same assessments as on the Day 8 and Day 21 visits, respectively, will be performed. In case the subject's legally acceptable representative(s) withdraw consent during the treatment or follow-up phase, an optional Withdrawal and Safety Follow-up Visit will be offered. At these optional Withdrawal and Safety Follow-up Visits, the same assessments as on the Day 8 and Day 21 visits, respectively, will be performed.
- Screening/predose assessments can only start after signing of the ICF and before randomization. All screening/predose procedures should take place prior to the first study drug intake.
- If feasible for the study site and if allowed per local regulations, home visits are allowed instead of on-site visits (although on-site visits are preferred).

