- ee. Blood samples for determination of JNJ-53718678 concentrations will be collected through finger prick or heel stick on Days 3 and 5 at a random timepoint (predose or postdose) during the visit. Detailed information on sample collection is available in Section 9.4. Leftover blood samples collected for other testing may be used for exploratory biomarker analyses, at discretion of the sponsor.
- ff. Adverse events related to the use of the biosensor reported during the substudy will be recorded in the eCRF of the main study.
- gg. At Day 1 and Day 3, ECGs should be obtained approximately one hour after administration of study drug. At Day 28, ECGs should be obtained in case abnormal ECGs at Day 21 or at discretion of the principal investigator. Anytime when it is clinically indicated or for confirmation of abnormal ECG findings, unscheduled ECGs should be obtained.
- hh. Levels of potassium and magnesium will be determined by the central laboratory. In case of hypokalemia or hypomagnesemia at screening or at Day 8, the levels of potassium and magnesium should be checked as soon as possible at the local laboratory and corrected to prevent cardiac disturbances. Appropriate clinical management per local SOC (including but not limited to checking the corrected values at local laboratory) may be required.
- ii. PK samples should be collected approximately one hour after administration of study drug (after the ECGs are obtained if applicable) at Day 1 and at least 4 hours after the AM and prior to the PM dosing on Day 3 or Day 5.

Note 1: Additional unscheduled visits in case of lab abnormalities, ECG abnormalities, need for clinical follow up of (an) AE(s) can be scheduled at the discretion of the investigator.

Note 2: Refer to [Attachment 10](#) for guidance on study conduct during the COVID 19 pandemic.

ABBREVIATIONS

AE	adverse event
ALT	alanine transaminase
AST	aspartate aminotransferase
aPTT	activated partial thromboplastin time
AUC	area under the RSV viral load-time curve
BCRP	breast cancer resistance protein
bid	twice daily
BM	bone marrow
BW	body weight
CI	confidence interval
C _{max}	maximum plasma concentration
C _{min}	minimum plasma concentration
COA	clinical outcome assessment (paper or electronic as appropriate for this study)
COVID-19	Coronavirus Disease 2019
CPE	complete physical examination
(e)CRF	case report form(s) (paper or electronic as appropriate for this study)
CV	coefficient of variation
CYP	cytochrome
DBP	diastolic blood pressure

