5. TREATMENT ALLOCATION AND BLINDING

Treatment Allocation

Procedures for Randomization and Stratification

Central randomization will be implemented in this study. Within each cohort (including the subcohort of Cohort 1), eligible subjects will be randomized 1:1:1 to receive either a low or a high dose of JNJ-53718678, or placebo. Those randomized to a placebo regimen will be subsequently randomized in a 1:1 ratio to receive either low or high volume of placebo. This results in an overall randomization scheme of 2:2:1:1 (low dose JNJ-53718678, high dose JNJ-53718678, low volume placebo, high volume placebo). Randomization will be based on a computer-generated randomization schedule prepared before the study by or under the supervision of the sponsor.

In the subcohort of Cohort 1, next to randomization to treatment group, within each treatment arm (high dose, low dose, placebo), the 6 subjects will be randomized 1:1 to 1 of 2 different PK sampling groups (see Table 4). In Cohort 1, next to randomization to treatment group, the first 12 subjects of each age group (subcohort not included) will be randomized 1:1 to 1 of 2 different PK sampling groups (see Table 4). Once 12 subjects of a particular age group have been randomized to the 2 different PK sampling groups, the investigator can assign the subsequently enrolled subjects to either of the 2 PK sampling groups, but preferably alternating between 2 different PK sampling groups at this site. In Cohort 2, PK samples will be collected as indicated in the [TIME AND EVENTS SCHEDULE](#).

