9.4.1. Evaluations

Blood samples for determination of JNJ-53718678 concentrations will be collected through finger prick or heel stick at the timepoints indicated in the [TIME AND EVENTS SCHEDULE](#). In the subcohort of Cohort 1, next to randomization to treatment group, within each treatment arm (high dose, low dose, placebo), the 6 subjects will be randomized 1:1 to 1 of 2 different PK sampling groups (see [Table 4](#)). In Cohort 1, next to randomization to treatment group, the first 12 subjects of each age group (subcohort not included) will be randomized 1:1 to 1 of 2 different PK sampling groups (see [Table 4](#)). Once 12 subjects of a particular age group have been randomized to the 2 different PK sampling groups, the investigator can assign the subsequently enrolled subjects to either of the 2 PK sampling groups, but preferably alternating between 2 different PK sampling groups at this site.

Table 4: Overview of Pharmacokinetic Sampling Windows for Cohort 1 Subjects

Pharmacokinetic Sampling Group	Visit Day 1	Visit Day 2	
	Time after dose intake at Visit 1	Time before dose intake at Visit 2	Time after dose intake at Visit 2
X	2 h – 5 h	-	30 min – 3 h
Y	5 h – 9 h	3 h – 1 min	-

For the subjects recruited to Cohort 2 after Protocol Amendment 4, PK samples will be collected approximately one hour after administration of study drug (after the ECGs are obtained if applicable) at Day 1 and at least 4 hours after the AM and prior to the PM dosing on Day 3 or Day 5.

Samples may also be used for the analysis of metabolites of JNJ-53718678 or endogenous markers for enzymes or transporters involved in the metabolism and distribution of JNJ-53718678, at the discretion of the sponsor. Blood samples collected for PK may additionally be used to evaluate safety or efficacy aspects that address concerns arising during or after the study period. Genetic analyses will not be performed on these samples. The subject's confidentiality will be maintained.

The following information needs to be recorded on the requisition form and/or eCRF: date and time of preceding study drug intake, date and time of PK blood sampling, fed status (yes/no, fed status defined as having a meal 30 minutes before or 30 minutes after dosing), and type of meal (milk vs. other).

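### On the Cohort 2 PK row of the Time and Events Schedule, footnote ee conflicts with footnote ii and Section 9.4.1 on sampling days and times and needs reconciling

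*Protocol*

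**What the plan says.** The table concerned is headed "COHORT 2 SUBJECTS RECRUITED AFTER PROTOCOL AMENDMENT 4", so everything in it applies to the twice-daily subjects now being enrolled.

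Its PK blood-sampling row carries two footnotes:

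- **Footnote ee, on the row label:** blood is "collected through finger prick or heel stick on Days 3 and 5 at a random timepoint (predose or postdose) during the visit". It then refers to Section 9.4 for detail.
- **Footnote ii, on the cells for Day 1 (plain mark), Day 3 and Day 5 (marks in parentheses):** "PK samples should be collected approximately one hour after administration of study drug (after the ECGs are obtained if applicable) at Day 1", and a second sample "at least 4 hours after the AM and prior to the PM dosing on Day 3 or Day 5".

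Section 9.4.1 gives the footnote ii rule for the same subjects: "For the subjects recruited to Cohort 2 after Protocol Amendment 4, PK samples will be collected approximately one hour after administration of study drug" on Day 1, then the Day 3 or Day 5 sample in the same window. Section 3.1 and the Synopsis (study design and pharmacokinetic evaluations) say the same.

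Section 5 points the other way, to the schedule: "In Cohort 2, PK samples will be collected as indicated in the" Time and Events Schedule. Section 9.4.1 also opens by referring to the timepoints given there.

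**The concern.** Two footnotes on one row give different instructions on which days to sample, how many samples to take and when. Both are current text. Footnote ee cannot be a rule kept for the earlier once-daily subjects, because the table heading excludes them.

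The timing has a stated purpose. The Amendment 4 rationale says the PK schedule was changed to obtain a sample at Cmax in each patient, for safety in relation to QT prolongation, and a sample in the distribution or elimination phase, for AUC and trough. The Amendment 5 rationale adds that a trough is determined by time after dosing rather than by the day. A sample taken at an arbitrary time secures neither. Sampling is sparse, a missed Day 1 sample cannot be recovered, and Section 1.2.4 commits to taking blood from these children only at carefully selected timepoints.

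**Working it through.** No sample size, power or error-rate figure is involved, so the check is a comparison of the texts.

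| Element | Footnote ee | Footnote ii, Synopsis, Sections 3.1 and 9.4.1 |
|---|---|---|
| Day 1 sample | not mentioned | one, about 1 h post-dose |
| Day 3/5 samples | two (Day 3 and Day 5) | one (Day 3 or Day 5) |
| Timing on Day 3/5 | any time in the visit, predose or postdose | at least 4 h after the AM dose and before the PM dose |
| Total samples | 2 | 1 + 1 = 2 |

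There are three ways a site could act:

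1. **Follow footnote ii or Section 9.4.1.** Two samples, both as intended.
2. **Follow both footnotes.** Days 1, 3 and 5 give three samples, so 3 − 2 = 1 puncture more than footnote ii asks for.
3. **Follow footnote ee alone.** Two samples, neither of them on Day 1, and neither assured to fall in the Day 3/5 window. Of the two intended samples, none is guaranteed.

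In the third case, other instructions make a sample outside the window plausible. Section 9.1.1 prefers assessments around dosing to be done before the dose on days after Day 1. Footnote gg puts the Day 3 ECG at about one hour post-dose. A sample taken alongside either would be predose or early.

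**How many subjects.** Cohort 2 is planned at about 150, with a maximum of 300 (Section 3.1). The protocol does not say how many were recruited after Amendment 4, so these figures are upper limits. Under Section 9.4.2 only active-arm samples are assayed. With 1:1:1 randomization, concentration data could be affected in at most 150 × 2/3 = 100 subjects, or 300 × 2/3 = 200 at the maximum size. An extra puncture could affect placebo subjects too.

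**The case against.** The strongest reply is that the intended rule is easy to find. The Day 1 cell is marked without condition and carries footnote ii. Footnote ee leaves Day 1 out but does not forbid it, and it sends the reader to Section 9.4, where the footnote ii rule is set out. Attachment 10 also lists PK sampling among the Day 1 assessments that may be done at home. One phrase stands against all of this. That is correct, and it lowers the likelihood of error. It does not remove the conflict, because Section 5 makes this schedule the reference for Cohort 2 PK sampling.

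A reader might infer more than the documents support:

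- **That the two footnotes cannot both be followed.** Sampling on Days 1, 3 and 5 within the footnote ii window would largely satisfy both, since footnote ee permits predose or postdose. What cannot be reconciled is two Day 3/5 samples against one.
- **That subjects would have no Day 1 peak-region sample.** This requires a site to disregard the marked Day 1 cell. Nothing shows that any site has done so.
- **That the QT risk plan needs both samples.** Only the Day 1 sample is tied to Cmax and QT. The later one serves AUC and trough. The QT mitigation list in Section 1.2.5 does not include PK sampling, and the discontinuation rule in Section 10.3 rests on ECGs.
- **That a specified exposure-QTc estimate would be lost.** Section 11.7 only explores exposure relationships, in tables or graphs. Section 11.6 says population PK may be performed and may pool other studies, and Section 9.4.2 lists Cmax only as a possible parameter. The model uses actual sampling times, so a mistimed sample still carries information, though not at the intended part of the profile.

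**Conclusion.** The point holds as an internal inconsistency in operative site instructions. Footnote ee disagrees with footnote ii on the same row and with the Synopsis, Section 3.1 and Section 9.4.1. The consequence is a risk and not a demonstrated loss: one unneeded Day 3/5 sample per child, a sample outside the AUC/trough window, or an overlooked Day 1 sample. How often this happens depends on how many sites work from footnote ee, which the protocol cannot show.

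The reach is limited to PK data quality, the exploratory exposure-response work and sampling burden. The primary viral-load analysis does not use these samples. The one-hour ECGs on Days 1 and 3 are fixed separately by footnote gg. The point is worth correcting because the affected samples have a stated purpose and the correction is very small.

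**What to change.** Reconcile footnote ee with footnote ii and Section 9.4.1. One way is to delete the phrase "collected through finger prick or heel stick on Days 3 and 5 at a random timepoint (predose or postdose) during the visit" from footnote ee, apart from the collection method, so that for days and times it only cross-refers to Section 9.4.1. Send sites a short clarification naming the single rule in force, so that the correction does not wait for the next amendment.

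Section 9.4.1 already requires the dates and times of the preceding dose and of the sample to be recorded. The sponsor can therefore check from existing data whether any Cohort 2 subject lacks a Day 1 sample, has both a Day 3 and a Day 5 sample, or was sampled outside the window.

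The cost is a one-line correction and a site memo. No design element, sample size or primary analysis changes.

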1. INTRODUCTION

Respiratory syncytial virus (RSV), a negative-stranded ribonucleic acid virus belonging to the *Pneumoviridae* family, is considered the most important virus causing acute lower respiratory tract infection (LRTI). Two subtypes of RSV have been identified ie, subtypes A and B that generally co-circulate simultaneously, although with a higher prevalence of subtype A.⁸ The RSV season occurs during winter months in regions with temperate climates in the Northern and Southern Hemispheres and throughout the year or with peaks semi-annually in tropical regions.^{1,30}

In most patients, RSV usually results in upper respiratory tract infections eliciting “common cold”-like symptoms, which might last up to 2 weeks and are usually self-limiting but hospitalization does occur, with hospitalizations in the United States for RSV estimated at 55.3/100,000 person-years between 1993 and 2008 for all ages.³¹ RSV infection can cause considerable morbidity and mortality in certain patient populations such as infants²² where RSV can lead to lower respiratory tract infection (LRTI), with severe respiratory compromise. In children ≤ 3 years of age, the clinical presentation of RSV disease is linked to the anatomy of their maturing respiratory tract. RSV infection causes inflammation and necrosis of the bronchiolar epithelial cells. The lumina of the bronchioles become obstructed from edema of the airway wall, increased mucus secretion, sloughed epithelium, and cellular debris. The small-diameter airways in infants are particularly vulnerable to obstruction. Such obstruction of bronchioli may lead to bronchiolitis and can cause respiratory distress.^{20,21}

RSV is a major cause of hospital admissions and death in young children worldwide.^{22,25} Infants born prematurely or close to the RSV season and/or suffering from bronchopulmonary dysplasia or congenital heart disease have the highest risk of developing severe RSV-related acute LRTI.⁹ In 2015, there were approximately 33.1 million RSV-LRTI episodes in 0-4-year-old children globally, which resulted in approximately 3.2 million hospitalizations and 59,600 deaths for this age group. Approximately 45% of these hospital admissions and in-hospital deaths occurred in children younger than 6 months.²⁶

On the other hand, among children <5 years of age with RSV infection, 97.7% present for medical care as outpatients in emergency departments and in pediatric practices, while 2.7% require hospitalization.¹¹ It has been estimated that 2.2% (1.7 million visits) of all US primary care visits of children <5 years of age in the year 2000 resulted from RSV infection.¹⁸ These rates of visits for RSV-associated acute respiratory infections suggest that a major proportion of the burden of RSV results in outpatient visits among children beyond infancy.¹¹

Despite the large medical and economic burden, no vaccines or antiviral agents have been approved for the prevention or treatment of RSV infection in either adult or pediatric populations.^{2,24} In hospitalized patients, the current treatment of RSV infection is often limited to supportive care, consisting of supplemental oxygen therapy, nutrition, fluids, and, in some cases, mechanical ventilation.^{7,28} In an outpatient setting, the standard of care is limited to symptomatic treatment of the flu-like manifestations of the disease. Overall, the unmet medical need (prophylactically and therapeutically) is substantial in both children and adults with RSV infection, whether hospitalized or outpatients.

The window between the onset of clinical symptoms after RSV exposure followed by infection (Day 3) and peak viral load (Day 6) is on average 3 days in children and adults^{4,5,6}, which is sufficiently long to initiate treatment, if diagnosed early. As most hospitalized subjects with RSV infection already had presented to a primary healthcare provider (HCP) 1 or 2 days prior to hospitalization^{6,29}, there is indeed an opportunity to initiate treatment in these subjects in a community setting ie, at the point of the initial HCP contact. Also, studies in the adult and pediatric population have demonstrated that RSV viral load and severity of disease symptoms are closely correlated,^{4,5,6} except for 1 recent study that did not confirm this correlation.²⁷ Together, these data suggest early initiation of treatment in outpatients is possible, and could result in a decrease of the viral load, syncytia formation, and in inflammatory reactions following RSV infection, and hence may improve disease outcomes and shorten the duration and/or severity of the disease, potentially avoiding hospitalization.

Enveloped viruses like RSV have a complex membrane fusion machinery that includes a fusion protein that enables the deposition of the viral nucleic acid genome into the host cells and initiates their replication.^{3,19} JNJ-53718678 is an investigational RSV specific fusion inhibitor belonging to the indole chemical class and is under development for the treatment of RSV infection. The study drug shows in vitro activity against a panel of viruses belonging to both the RSV subfamilies A or B. In addition, antiviral activity of JNJ-53718678 was demonstrated during clinical studies in healthy adults inoculated with RSV (Study 53718678RSV2001) and in pediatric subjects hospitalized due to RSV-infection (Study 53718678RSV1005).

For the most comprehensive nonclinical and clinical information regarding JNJ-53718678, refer to the latest version of the Investigator's Brochure (IB) and Addendum for JNJ-53718678.^{17,16}

The term "sponsor" used throughout this document refers to the entities listed in the Contact Information page(s), which will be provided as a separate document.

